1. TITLE

Glycemic Optimization On Discharge from the Emergency Room (GOOD-ER) program

2. EXTERNAL IRB REVIEW HISTORY*

NA

3. PRIOR APPROVALS:

NA

Conflict of Interest (COI):

The Study Investigators have no COI to disclose.

Clinical Engineering Department:

The continuous glucose monitor and reader have been inspected and approved by clinical engineering.

Biohazardous Agents:

NA

Radiation:

NA

Students as Subjects:

NA

Data Science Core & Recruitment Core:

The Data Science Core has been consulted and their services are not required for this protocol.

UMCCTS Protocol Review Committee (PRC)

This project has been reviewed by the PRC and approved for submission to the IRB. Several revisions were made to this ISP in response to the PRC comments. A document describing the PRC comments and the changes made is also included with the application.

4. OBJECTIVES*

Our goal is to help people with diabetes who are treated and then discharged from the emergency department (ED) achieve better health outcomes. Specifically, we are interested in determining whether or not continuous glucose monitoring after ED discharge is useful.

People living with diabetes, particularly those from disadvantaged socioeconomic backgrounds, frequently seek medical care through the emergency department (ED), but coordinated longitudinal follow up is often lacking. Almost 1 in 10 ED visits are related to diabetes (1), and rates of diabetes-related ED utilization are negatively correlated with household income (2, 3). Being evaluated in the ED can be a powerful motivator for patients, but this window of opportunity can be missed if patient activation is low or if access to ongoing medical care is limited. Interventions designed to improve continuity between the ED and diabetes specialty care have shown promise in terms of reducing hospitalizations and medical expenditures (4), but even at institutions with these programs in place, recurrent diabetes-related ED visits continue to be a problem (5). Overall, diabetes care for people in the ED remains fragmented and poorly studied.

As we attempt to help people seeking care for diabetes in the ED, we plan to study the potential role of continuous glucose monitoring (CGM) in this novel context. In the outpatient setting, CGM has been shown to cause clinically significant reductions in hemoglobin A1c as well as hyper- and hypoglycemia (6-8). It can also improve a patient's self-management skills and understanding of how food and activity affect blood sugar (9). CGM use, however, has never been studied as a tool to help people being discharged from the ED. It will be valuable to assess its usefulness in this setting, as patients are at high risk of recurrent hyper- or hypoglycemia during this transitional window (10, 11) and may be more engaged than at other times.

Our plan is to conduct a randomized controlled trial of unblinded CGM among people with diabetes who are discharged home after being treated in the ED for diabetes-related emergencies. In conjunction with research assistants, ED clinicians at the University Campus, Memorial Campus, Marlborough Campus, Clinton Campus, and Leominster Campus will identify patients with diabetes (type 1 or 2) and hyper- or hypoglycemia who would benefit from follow up in the UMass Diabetes Center of Excellence (DCOE). The ED physician will place a referral, if necessary, and study staff will help arrange this follow up, scheduling an appointment within 2-3 weeks. In addition to this care coordination, half of the participants will receive a CGM placed by the patient or study staff in the ED, and all patients will receive written instructions about how to handle recurrent hyper- or hypoglycemia.

The primary outcomes will be the rate of attendance at the follow-up visit and be the change in diabetes-related quality of life as measured by the PAID-5 scale and the DDS. We hypothesize that having a CGM will decrease the no-show rate and increase clinic attendance and improved diabetes-related quality of life. Secondary outcomes will include hemoglobin A1c levels over time, ED utilization, emergency medical services utilization, hospitalizations, and major cardiovascular events within 6 months. Finally, we will assess provider satisfaction in the DCOE via a brief survey.

Focusing on a common but rarely studied clinical problem – the ED-to-clinic transition for people with diabetes – this project will promote inter-departmental collaboration between the ED and the DCOE and will directly improve care for people with diabetes, particularly those from disadvantaged groups. In addition to improving care coordination, we will rigorously assess the

usefulness of CGM in a novel context, generating preliminary data for future work and serving as an example for other medical systems regionally and around the world.

5. BACKGROUND*

Emergency physicians and endocrinologists agree that the emergency department (ED) is not an optimal venue for delivering longitudinal medical care for people with diabetes, but diabetes-related ED visits remain common. In the United States in 2010, for example, approximately 10 percent of all ED visits – over 12 million in total – were for diabetes-related problems, the majority of which did not require hospital admission (1). Seeking emergency care for diabetes is associated with lower income and socioeconomic status (2, 3, 12), and this lack of continuity of care is associated with worse outcomes (13-15). Programs designed to improve care coordination between the ED and subspecialty diabetes care have shown promise (4, 5), at least in terms of reducing ED visits and expenditures, but significant works remains to be done, especially in terms of patient-centered outcomes.

Over the last decade, the emergence of continuous glucose monitoring (CGM) technology has changed how many people with diabetes manage their disease, but the ideal role for these devices is still being established. In outpatient settings, randomized trials have shown that CGM reduces hemoglobin A1c as well as hyper- and hypoglycemia (6-8, 16). There is also evidence that CGM use is associated with a reduction in hospitalizations and emergency diabetes-related events (17). From the patient perspective, CGM has been shown to improve diabetes-related quality of life (18) and diabetes self-management skills (9). Most of these studies, however, were conducted in ambulatory settings. CGM has never been studied as a tool to help people seeking diabetes-related care in the ED, a vulnerable population in which the potential benefit could be high.

At UMass Memorial Medical Center, we have an opportunity to implement and study new approaches to caring for people with diabetes-related emergencies. The UMass ED and the DCOE both serve large numbers of patients and exist within an academic environment conducive to patient-focused research. At the University Campus in 2019, over 1,000 people were treated for hyper- or hypoglycemia and then discharged home without being admitted to the hospital. Our goal is to help these patients avoid repeat ED visits and poor glycemic outcomes by bridging the gap between the ED and the DCOE. We believe that CGM during the high-risk period of time after ED discharge will help patients avoid recurrent glycemic problems while reducing their diabetes-related distress and helping their outpatient providers.

In addition to helping patients at UMass, we hope to pave the way for implementation of such programs on a broader scale, as there is great agreement among stakeholders that improvement is needed. Emergency physicians are motivated to reduce the number of patients seeking emergency care, as waiting rooms at UMass and elsewhere are frequently crowded, and diabetologists know that continuity of ambulatory care is in the best interests of their patients. Health systems work to keep expenses down, and of course, most importantly, patients prefer to avoid the ED when possible. We believe all these factors will make our program valuable and exciting to other systems.

The work we propose is innovative both in terms of its subjects and its methods. The population of people seeking care in the ED is more disadvantaged than the population as a whole, and it is

also a population that is studied far less often than outpatient populations. Most diabetes-related studies focus on patients affiliated with certain hospitals or group practices, potentially missing people who lack a secure relationship with longitudinal care. Our project is designed to improve outcomes for this large, at-risk group.

Our desire to study the effectiveness of CGM during the ED-to-clinic transition is also novel. The existing CGM literature is skewed towards studies of well-connected patients being followed as outpatients. We feel, however, that CGM could have value for other patients, such as those in the ED population who have already demonstrated their risk for severe hyper- or hypoglycemia. We will be the first group to rigorously study CGM as tool to help people being discharged from the ED, and thus our work will lay groundwork for future studies, hopefully both here at UMass and elsewhere.

6. INCLUSION AND EXCLUSION CRITERIA*

Patient Subjects:

Inclusion Criteria:

- Age 18 years or older
- Patients must be preparing for discharge from the emergency department after being treated for either hyperglycemia or hypoglycemia
- Patients must be either new referrals to the DCOE or existing DCOE patients in need of post-ED follow up
- Patients must have type 1 or type 2 diabetes
- Patients must be able to provide informed consent
- Patients must be fluent in English or Spanish

Exclusion Criteria:

- Current CGM use
- Need for hospital admission
- Upcoming computed tomography (CT) or magnetic resonance imaging (MRI) studies within 2 weeks, as these imaging modalities could potentially affect CGM performance
- Pregnant patients, as the device is not approved for pregnancy
- Any altered mental status, which would limit a patient's ability to consent to the study
- Patients who already have a longitudinal relationship with an outside endocrinologist
- Patients who have not been referred to the DCOE
- Prisoners
- Patients under age 18 years
- Patients who do not speak English or Spanish fluently

Justifications for Criteria:

-Our intervention targets patients with diabetes who are treated and discharged from the emergency department after being treated for either hyperglycemia or hypoglycemia.

-We will translate consent materials and patient instructions into Spanish. No additional languages are included as the CGM being used for the study and its associated reader only has English and Spanish menus and instructional manuals.

-Prisoners represent a special population that is routinely excluded from similar research studies. They represent an inaccessible population.

-Patients under eighteen are typically treated by pediatric endocrinologists and have different care regimens that are beyond the scope of this study.

-Pregnant women will not be included in this arm of the study as the CGM being utilized for this study is not FDA approved for use in pregnant women.

Provider Subjects:

Inclusion criteria for provider subjects will consist of licensed independent providers (NP, PA, MD, DO or MBBS) who provide subspecialty diabetes care to a patient subject enrolled in the study. Pregnant women may be included in this cohort as this study arm entails less than minimal risk and the study activities have no impact on pregnancy.

Exclusion criteria: Adults unable to consent, subjects under 18 and prisoners will be excluded from this study. Any subject that does not meet the inclusion criteria will be excluded. Trainees, including medical students, resident physicians, and fellows will be excluded from this study.

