- **Diabetes Center of Excellence Care Coordination:** Study Staff will follow up with ED provider to ensure that patients' have clinically indicated referral to diabetes center of excellence

→ **Appointment scheduling:** RA will make an appointment for the patient before ED discharge, if possible. If this is not possible, RA will contact the patient after discharge to arrange a follow-up appointment.

Outpatient Blood Sugar Monitoring: The CGM will be worn on the participants' upper arm continuously for 14 days (or until it falls off or the patient decides to remove it)

[figure not shown]
Visit #1 (~Day 14-21 Post-Discharge of patient subjects)

- **Documents:**
 - **Visit Data (RA facing)**
 - **Problem Areas in Diabetes (PAID-5) scale/Diabetes Distress Scale and supplemental questions**
 - **Fact sheet for provider subjects**
 - **Provider satisfaction survey**
- **CGM Data:** Biosensor data will be downloaded and reviewed
- **Material Collection:** Study Staff will collect CGM readers
- **Compensation:** Participants will be offered \$10 worth of gift cards to a retail store for completing visit #1.
- **Provider Survey:** immediately following an encounter with a patient subject, the provider taking care of each patient will be contacted by the study team as potential provider subjects. Potential provider subjects subsequently will be sent an email solicitation to participate in a Redcap survey. A fact sheet will be provided with that email. The survey will consist of 4 questions pertaining to their satisfaction with patient subject care coordination and/or their CGM utilization. Providers may be sent multiple surveys if they see multiple subjects who are enrolled in the study. This is the only involvement of the provider subjects.
- **No Shows:** *RAs will reach out to subjects who miss their follow-up appointment to (1) help them reschedule and (2) ask that they fill out the post-intervention questionnaire via an online link (or mailed paper copy or via phone, if desired)*

Follow up Data Collection (~6 months Post-Discharge)

- **Documents:**
 - **6 month follow up datasheet**
- **Data Collection:** The study team will query the EHR to collect follow up data points about enrolled subjects

Figure 1: Procedural Flow Sheet

t

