Data for analysis will be downloaded directly from REDCap and converted to SAS datasets or R data frames for analysis. The downloaded datasets will be deidentified and are HIPPA as well as 21 CFR Part 11 compliant.

Provider Data:

We will present the data from the provider surveys in a descriptive fashion. For example, we will report the percentage of patients in the CGM arm whose provider found the data useful. We will also do subgroup analyses. Potential subgroups include the type of diabetes, whether or not the diabetes diagnosis is new, and whether or not the participant presented to the ED with hypo- or hyperglycemia.

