18. VULNERABLE POPULATIONS*

No vulnerable populations will be included in this study. Pregnant patients, patients under 18, adults unable to consent, and prisoners are all excluded.

In the provider subject cohort, no subjects will be approached who are directly or indirectly supervised by any member of the study team.

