23. RESOURCES AVAILABLE

Study Staff: All Study Staff members are up to date on CITI certification and are aware that this training must be renewed every three years. They will conduct this research in accordance with the current, IRB approved protocol.

- **Study Investigators:**
 - **Principle Investigator (PI):** The PIs are a board-certified Endocrinologist and Emergency Medicine physician with experience in human subjects' research.
 - **Responsibilities:** The PIs will be responsible for overseeing the entire study including, but not limited to (1) dissemination of the research protocol to all Study Staff; (2) recruitment; (3) enrollment; (4) data collection; (5) data analysis; and, (6) dissemination of results. The PI will ensure all Study Staff are adequately trained and monitor their progress to ensure they are following the protocol.
 - **Co-Investigators (Co-Is):** The Co-Is are physicians from the departments of Emergency Medicine, and Endocrinology
 - **Responsibilities:** The Co-Is will assist the PI with all aspects of the study including, but not limited to: (1) recruitment; (2) enrollment; (3) administering questionnaires; (4) interpretation of results; and, (5) preparation of the resulting manuscripts.
- **Additional Study Staff Roles:**
 - **Research Assistants (RAs):** The RAs will have basic training in research methods and human subjects' research, as well as a bachelor's degree in a human science field or equivalent.
 - **Responsibilities:** They will be trained by the PI and Research Coordinator to complete most aspects of the study including, but not limited to: (1) explaining the study to eligible individuals; (2) obtaining informed consent; (3) training participants in the use of the CGM sensor and reader; (4) how to conduct a chart review; (5) data handling; (6) arranging follow-up visits; and, (7) administering questionnaires.
 - **Research Coordinator (RC):**
 - **Responsibilities:** In addition to the responsibilities described for the RAs, the RC will train and monitor the RAs and assist with regulatory requirements and communications with the IRB.

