25. LOCAL NUMBER OF SUBJECTS

We expect to recruit patient 200 patients in the one-year period (100 in each arm). As per the power analysis described in section 13, this will allow us to measure our described outcomes. We expect to recruit approximately 8 provider subjects.

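### The provider survey does not exclude study-team members, so an endocrinologist investigator could be one of about 8 clinicians rating the programme, and the reporting plan does not separate such ratings

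*Combined protocol and SAP*

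**What the plan says.** Section 6 (Provider Subjects) defines eligible raters as "licensed independent providers (NP, PA, MD, DO or MBBS) who provide subspecialty diabetes care to a patient subject enrolled in the study". It excludes adults unable to consent, minors and prisoners, and adds: "Trainees, including medical students, resident physicians, and fellows will be excluded from this study". Section 18 adds that in this cohort "no subjects will be approached who are directly or indirectly supervised by any member of the study team". None of these rules mentions members of the study team.

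On who the investigators are, Section 23 says "The PIs are a board-certified Endocrinologist and Emergency Medicine physician" and "The Co-Is are physicians from the departments of Emergency Medicine, and Endocrinology".

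On who is surveyed, Section 11 says that after an encounter "the provider taking care of each patient will be contacted by the study team as potential provider subjects". The same paragraph allows one provider to receive several surveys if they see several enrolled patients. Section 25 gives the size of the pool: "We expect to recruit approximately 8 provider subjects".

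On reporting, Section 10 lists provider satisfaction, including whether the CGM data helped for each patient, with the study endpoints. Section 13 (Provider Data) describes a descriptive summary and gives as its example that "we will report the percentage of patients in the CGM arm whose provider found the data useful", followed by subgroup analyses. It does not separate raters by whether they belong to the study team.

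**The concern.** The survey asks clinicians for a judgement on the programme and on the value of CGM data. In Section 5 the investigators state their belief that CGM will help outpatient providers. If an investigator is also the treating clinician, that person is asked to judge their own hypothesis. Every rater knows whether CGM was used, so lack of blinding does not set investigators apart. Their stake in the answer does.

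With about 8 raters, each of whom may return many surveys, one person can carry a visible share of the reported percentage. Under the present wording, a reader of the results could not tell how much of that percentage came from the study team.

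**Working it through.** **Step 1: is a study-team member eligible?** Set the rules side by side.

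- Section 6, inclusion: turns on licence and on giving subspecialty diabetes care to an enrolled patient. An endocrinologist investigator who sees a study patient in the diabetes clinic meets it.
- Section 6, exclusions: adults unable to consent, minors, prisoners and trainees. Investigators are not listed.
- Section 18: bars people supervised by team members. It does not bar the members.
- Section 27: staff directly involved in recruiting and consenting participants stay out of those participants' clinical care. This works patient by patient. Section 23 gives recruitment and enrolment to investigators, but also gives explaining the study and obtaining consent to research assistants. For a patient consented by a research assistant, the rule does not stop an investigator from treating that patient and then being surveyed.

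The text therefore permits a study-team member to be a rater.

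**Step 2: how much weight does one rater carry?** The inputs from Section 25 are about 8 providers and 100 patients in the CGM arm. The 8 is an expectation without a derivation, so there is no calculation in the plan to reproduce. Assuming equal caseloads:

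- Share per provider = 1/8 = 12.5% of ratings.
- CGM-arm encounters per provider = 100 × attendance / 8. This is 100/8 = 12.5 at full attendance, 80/8 = 10 at 80%, and 67/8 = 8.4 at 67%. The last two rates are the target and the comparison value in Section 13; neither is a forecast.

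**Step 3: how far could the percentage move?** Let k be the number of investigators among the 8, r_I the proportion of their patients for whom they find the data useful, and r_O the same proportion for other providers. Then

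reported = (k/8) × r_I + (1 − k/8) × r_O, and the shift from r_O is (k/8) × (r_I − r_O).

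The documents give no value for k, r_I or r_O. The values below are assumptions.

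| k | r_O = 60%, r_I = 100% | r_O = 60%, r_I = 90% | r_O = 80%, r_I = 100% |
|---|---|---|---|
| 0 | 60% | 60% | 80% |
| 1 | 0.125 + 0.875 × 0.60 = 65% | 0.1125 + 0.525 = 63.75% | 0.125 + 0.70 = 82.5% |
| 2 | 0.25 + 0.75 × 0.60 = 70% | 0.225 + 0.45 = 67.5% | 0.25 + 0.60 = 85% |
| 3 | 0.375 + 0.625 × 0.60 = 75% | 0.3375 + 0.375 = 71.25% | 0.375 + 0.50 = 87.5% |

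The shift is zero if no investigator is a rater, or if investigators rate as others do.

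**The case against.** The strongest reply is that the key fact is absent. No section says that any investigator sees study patients at the follow-up visit, or that any is counted among the 8. Section 27 also limits self-rating for patients whom an investigator personally recruited and consented. The procedure in Sections 11 and 24, in which the team identifies the treating provider and emails a solicitation with a fact sheet, reads more naturally as an approach to people outside the team. All of this stands. It makes the gap a possibility that the text leaves open, not a planned practice.

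A reader might infer three stronger things that the documents do not support.

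- That self-rating will occur and will bias the result upward. Neither its occurrence nor its size is documented.
- That the supervision rule raises the investigators' share by removing their juniors. Trainees are already excluded in Section 6, nothing shows that any licensed clinic provider is supervised by the team, and the 8 may already allow for the rule. Its place under vulnerable populations suggests protection from pressure, not selection of raters.
- That the percentage will be taken over returned surveys yet presented as a percentage of the arm. Read literally, Section 13 already uses the CGM arm as its denominator. What it leaves unsaid is how patients with no visit or no returned survey are counted, and that needs only a clarification.

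It is also fair to say that little hangs on this survey. It is descriptive, with no test, alpha or sample size attached.

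**Conclusion.** The point holds as a gap in eligibility and reporting. Trainees and supervised staff are excluded, study-team members are not, and Section 27 closes the gap only for patients whom the member recruited and consented. Whether any investigator would be a rater, and for how many patients, cannot be learned from the documents.

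With 60% and 100% as the assumed ratings and equal caseloads, each investigator among 8 raters would add 5 percentage points (0.125 × 0.40). The shift would be smaller with a narrower difference in ratings, and absent with no investigator raters. These figures show sensitivity and do not estimate bias. No primary outcome, error rate or power figure is affected. This is a cheap improvement to a secondary, descriptive result.

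**What to change.** - In REDCap, record for each provider survey whether the respondent is a member of the study team.
- In Section 13 (Provider Data), make the usefulness percentage from providers outside the study team the main figure and print the all-rater figure beside it. Use the same split in the subgroup summaries.
- With both figures, give the number of raters, the number of surveys returned and the number of patients randomised to CGM, so that the denominator is plain.

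Excluding study-team members outright would also close the gap, but would lose ratings that can be kept and labelled.

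The cost is one data field and a short addition to the reporting text. The main figure would rest on fewer rated encounters. For example, with 2 investigators among 8, equal caseloads, 80 attenders in the CGM arm and every survey returned (all assumed), it would use 80 × 6/8 = 60 ratings, and the all-rater figure would still use 80.
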